6.1 Patient registration/randomisation procedure

At the point of randomisation participants will be automatically registered on to the trial using the electronic data capture (EDC) system. Randomisation is after the online consent, the screening process and after the online baseline assessment. There is a two-part consent process which in the first part asks for permission to screen and take part in the assessment. The second part of consent with agreement sought to take part in the study is taken prior to baseline assessment. Participants can stop the assessment at any stage and be emailed a link to return the screening website. this allows them to have time to consider the participant information which they have read on screen and which is emailed to them. The email link will be live for 14 days. After this time the participant will need to contact the site to ask for the link to be reset.

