8.10 Trial assessments

Assessment will take place at baseline (start of treatment) and then at 6 weeks post baseline (equating to end of treatment) and 12-weeks post baseline. The 3-month follow up will be the primary endpoint. All assessments will be through EXCTU managed EDC system. Only if participants have not responded to email and text prompts to complete their follow ups at 6 and 12 weeks will they be contacted by phone and asked to provide the primary outcome measures only on the telephone. The results of the assessments are only to collect research data for the trial and will not be provided to medical practitioners. The only exception to that would be if a participant indicates suicide risk and asks us to provide their assessment results to their medical practitioner. They would need to give written consent for this and provide us with the contact details to do so. See risk protocol in Appendix.

At the end of treatment, participants that have received the sbLICBT resiliency intervention will receive an email asking them to participate in an acceptability focus group and Section 12 of the protocol provides further information on this.

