When and How Much	First delivery from October 2022 (revised to June 2023). Following the initial group session, participants will be encouraged to engage with the intervention on their own over the next 6 weeks. It will be emphasised that engaging for a manageable amount of time on a regular basis is better than trying to use the intervention for a long period of time periodically. However, the exact amount of time the participant engages with the intervention will be determined by them. To recruit 120 participants will require 3 iterations (30 sbCBT and 30DTC) per iteration, with the final DTC group receiving the intervention outside of the study.
Tailoring	The intervention has been co-produced with undergraduate students for a population of university students.
Modifications	The intervention used within the study is a modification of a previous intervention developed for university students. Modifications include removing 'resiliency' from the title and changing to 'Bounce Back', alongside reducing the frequency of the term 'resiliency' in the text itself.
How Well	Fidelity to the email support protocol will be measured by comparing written support emails to a fidelity checklist informed by an e-mail support protocol (Hadjistavropoulos et al., 2018).

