9.2 Delayed Treatment Control (DTC)

Participants randomised into the DTC will receive the intervention when those initially randomised into the intervention arm have completed the 6-week intervention.

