13.3 Recording and reporting of SAEs, SARs AND SUSARs

[figure not shown]
All serious adverse events that are trial or treatment related will be recorded and immediately reported to the Chief Investigator and within 1 working day (24 working hours) to the ExeCTU Trial Manager. If these are also classed as unexpected, they will be reported to the relevant ethics committees.

We will, in line with other complex intervention studies, monitor non-serious adverse events, serious adverse events that are not trial or treatment related, serious deterioration, and active withdrawals from treatment, with specific questions in the follow-up and in response to specific participant-initiated reports. Symptoms of depression or anxiety will not be defined as adverse events unless suicidal ideation, plans or an attempt has been made. The reporting period for all events and reactions will be from referral to 12weeks post baseline follow-up. Data on any adverse events will be collected by a member of the research team at each assessment and entered directly into the EDC.

The SAE form will capture the following data:

- Date and time of onset
- Date and time investigator became aware
- SAE category
 - o Death i.e. (homicide, suicide, accident, illness, all appropriate options) etc.)
 - Life threatening i.e. (suicide attempt, serious assault, self- harm)
 - o Hospitalisation or prolongation of existing hospitalisation or referral to crisis team
 - Persistent or significant disability or incapacity i.e. (include development of problematic substance/ alcohol abuse; onset of new Axis I disorder)
 - Congenital anomaly or birth defect
 - Other i.e. (potentially dependent life events, e.g. job loss divorce)
- The intensity will be specified as mild, moderate or severe
- The SAE will be determined as intermittent or continuous
- The SAE will be determined as expected or unexpected
- The SAE outcome will be determined as resolved with a date provided, resolved with sequelae, ongoing (follow ups to the SAE will be provided when there is a change to report in participants condition) or died (if died the cause of death will be specified)
- The SAE relationship to the study or trial procedures will be determined as not related, unlikely to be related, possibly related, definitely related or unknown
- A detailed description of the event will be provided and this field will also be used to
 document the dates and number of attempts made to contact a participant by phone and/or

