13.4 Responsibilities

Researchers at central site (University of Exeter) to check for SAEs, AEs and ARs when participants complete treatment or at follow-up, potentially in response to automated feedback from website.

Chief Investigator (CI) is responsible via liaison with research team at central site for:

- 1. Ensuring that all SAEs are recorded in EDC and reported to the ExeCTU Trial Manager within 24 working hours / 1 working day of becoming aware of the event and provide further follow-up information as soon as available.
- 2. Ensuring that SAEs are chased with ExeCTU Trial Manager if a record of receipt is not received within 2 working days of initial reporting.
- 3. Ensuring that AEs and ARs are recorded and reported to the ExeCTU Trial Manager in line with the requirements of the protocol.
- 4. Immediate review of all SUSARs.
- 5. Review of specific SAEs and SARs in accordance with the trial risk assessment and protocol as detailed in the Trial Monitoring Plan.

Sponsor (NB where relevant these can be delegated to CI and trial manager) is responsible for:

- 1. Central data monitoring and verification of AEs, ARs, SAEs, SARs and SUSARs according to the trial protocol within the database (EDC).
- 2. Reporting safety information to the CI, delegate or independent clinical reviewer for the ongoing assessment of the risk / benefit according to the Trial Monitoring Plan.
- 3. Reporting SAEs that are related to the trial and unexpected, by email to the research ethics committee.
- 4. Reporting SAEs that are related to the trial and unexpected, by email to the research ethics committee.
- 5. Reporting safety information to the independent oversight committees identified for the trial (Data Monitoring Ethics Committee (DMEC) and / or Trial Steering Committee (TSC)) according to the Trial Monitoring Plan.
- 6. Expedited reporting of SUSARs to the Competent Authority (MHRA in UK) and REC within required timelines.
- 7. Notifying Investigators of SUSARs that occur within the trial.
- 8. Preparing standard tables and other relevant information in collaboration with the CI and ensuring timely submission to the MHRA and REC.

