14.3.2 Assessment Website at Follow-up (6 and 12 weeks)

A recruit may indicate risk on the assessment website in follow-up assessments in response to questions about suicidality. If the participant scores 1-3 on question 9 of the PHQ9, then further questions to assess risk will automatically be presented.

PHQ9; Q9

Over the last two weeks, how often have you been bothered by any of the following problems? Thoughts that you would be better off dead, or of hurting yourself in some way?

Those scores would represent the answers several days (1), more than half the days (2) and nearly every day (3)

The further risk questions which will automatically be asked:

R1 In the last 2 weeks have you been experiencing regular thoughts about suicide?

R2 In the last 2 weeks have you had any intention to hurt or kill yourself?

R3 In the last 2 weeks have you made any plans to harm yourself or end your life?

If the participant answers yes to any of those questions then they would be automatically presented with the following risk page:

Follow up Website Automated Risk Message:

"Your responses to these questions suggest you have been thinking about suicide or about hurting yourself.

These kinds of thoughts can vary a lot. This may have just been a brief passing thought or reflect a sense of feeling trapped, but without any intention to do anything. These thoughts are relatively common and not that unusual in people who feel stressed. If you would like support with these thoughts, please contact your GP or relevant medical professional;

If you feel at high risk to yourself or others, please contact your GP immediately.

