APPENDIX

Appendix 1: Feasibility Outcomes

Feasibility	Outcomes				
_	people accessed study web site				
Number of	people complete screening				
questions					
Number of	people screened out	If Yes - Reason	Report by demographics		
Number of	people consented		Report by demographics		
Number of	people randomised		Report by demographics		
Blinding rar	ndomisation maintained	Yes	No		
Study arms					
sbLICBT	Number attended group session	Report by demo	graphics		
	Number completed baseline	Data completion of each item for each outcome			
	outcome measure	measure			
	Number completed end of	Data completion	n of each item for each outcome		
	treatment outcome measures	measure			
	Number completed final outcome	Data completion	n of each item for each outcome		
	measures 12-week post baseline	measure			
	Number of participants requesting support	Report by demo	graphics		
	Number of support episodes requested				
	Number of each type of support	Face to Face	e-mail		
	episode requested		C 111611		
DTC	Number completed baseline		'		
	outcome measure				
	Number completed outcome				
	measures at 6 weeks post baseline				
	Number completed final outcome				
	measures 12-week post baseline				
DTC move to sbLICBT	Number attended group session	Report by demo	graphics		
0.02.02.	Number completed baseline	Data completion	n of Number completed		
	outcome measure	each item for ea			
		outcome measu			
	Number completed end of	Data completion	n of Number completed		
	treatment outcome measures	each item for ea	•		
		outcome measu	re outcome measures		
	Number completed final outcome	Data completion	n of Number completed		
	measures 12-week post baseline	each item for ea	ich final outcome		
		outcome measu	re measures 12-week		
			post baseline		
	Number of participants requesting support	Report by demo	graphics		
	Number of support episodes				
	requested				
	Number of each type of support	Face to Face	e-mail		
	episode requested				

Brief Resilience Scale (BRS)

R	despond to each statement below by circling one answer per row.	Strongly Disagree	Disagree	Neutral	Agree	Strongly Agree
BRS 1	I tend to bounce back quickly after hard times.	1	2	3	4	5
BRS 2	I have a hard time making it through stressful events.	5	4	3	2	1
BRS 3	It does not take me long to recover from a stressful event.	1	2	3	4	5
BRS 4	It is hard for me to snap back when something bad happens.	5	4	3	2	1
BRS 5	I usually come through difficult times with little trouble.	1	2	3	4	5

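### Event reporting ends at 12 weeks post baseline with no provision for the delayed arm, leaving that arm no post-treatment observation and exposing its treatment weeks to any lag

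*Protocol*

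**What the plan says.** **Reporting window.** Section 13.3: "The reporting period for all events and reactions will be from referral to 12weeks post baseline follow-up". It does not say which baseline applies to DTC participants and gives them no separate period. The same section has event data gathered at every assessment, and section 13.4 asks researchers "to check for SAEs, AEs and ARs when participants complete treatment or at follow-up".

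**Scheduled checks.** The procedures schedule (Table 9 in section 8.11) has adverse-event assessments at 6 and 12 weeks and nothing later. Section 14.3.2 sets the follow-up suicide-risk questions at the same two times. Section 13.2 defines symptom deterioration only from baseline to week 6 and from week 6 to week 12.

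**Start of exposure.** Section 8.10 places assessments "at baseline (start of treatment) and then at 6 weeks post baseline (equating to end of treatment" and then at 12 weeks. Section 6.1 adds: "Randomisation is after the online consent, the screening process and after the online baseline assessment". After randomisation, an email gives the participant the date of the group session (section 8.6). For the delayed arm, section 9.2 says: "Participants randomised into the DTC will receive the intervention when those initially randomised into the intervention arm have completed the 6-week intervention".

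**Follow-up after the delayed start.** Appendix 1 has a block of rows headed "DTC move to sbLICBT", with a further baseline, an end-of-treatment measure and a 12-week measure. The feasibility table in section 10.1 has the same block.

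**Final delayed group.** The timing item of the TIDieR table in section 9.1 describes the iterations, "with the final DTC group receiving the intervention outside of the study".

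**The concern.** The window is anchored to study entry, while the delayed arm's exposure begins at least 6 weeks after it. The two arms therefore receive the same intervention but are watched for different lengths of time after starting it, and the delayed arm has no slack if sessions run late.

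Two uses of the safety data depend on this. Section 12.7 would discontinue the trial if evidence of harm from the intervention accumulates, and half of the planned recipients (60 of 120) are in the delayed arm. Section 14.3.2 uses the risk records to compare suicidality between arms, yet by week 12 the delayed arm may itself have been treated for up to 6 weeks. A table by randomised arm alone would then mix untreated and treated time in that arm.

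**Working it through.** The protocol gives no figure to reproduce here, so the check is timeline arithmetic.

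**Inputs**
- Window closes at week 12 after baseline (section 13.3), taking the only baseline that the procedures schedule shows.
- Intervention lasts 6 weeks (sections 9.1 and 9.2).
- Baseline is treated as the start of treatment and week 6 as its end (section 8.10 and Table 11).
- Lag L, in weeks: from the baseline assessment to the first group session, plus any gap before the delayed arm's own session. The protocol does not state it, so it is varied.

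**Formulas**
- DTC exposure runs from week L + 6 to week L + 12.
- DTC treatment weeks covered = max(0, 6 − L).
- DTC post-treatment weeks covered = max(0, 12 − (L + 12)) = 0 for every L ≥ 0.
- Immediate arm, if the whole lag falls before the first session and L ≤ 6: 6 treatment weeks covered and 6 − L post-treatment weeks.

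| L (assumed) | DTC exposure, weeks | DTC treatment weeks covered | DTC treatment weeks not covered | DTC post-treatment weeks | Immediate arm: treatment / post-treatment weeks |
|---|---|---|---|---|---|
| 0 | 6–12 | 6 | 0 | 0 | 6 / 6 |
| 1 | 7–13 | 5 | 1 (17%) | 0 | 6 / 5 |
| 2 | 8–14 | 4 | 2 (33%) | 0 | 6 / 4 |
| 3 | 9–15 | 3 | 3 (50%) | 0 | 6 / 3 |
| 4 | 10–16 | 2 | 4 (67%) | 0 | 6 / 2 |
| 6 | 12–18 | 0 | 6 (100%) | 0 | 6 / 0 |

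Over this range, observed time from the start of treatment is 12 − L weeks in the immediate arm and 6 − L in DTC, a constant difference of 6 weeks. The row L = 0 is the protocol's own timetable. The row L = 6 would put the immediate arm's end-of-treatment assessment at the start of its treatment, contrary to section 8.10, so it marks a limit and not an expectation.

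**If the window ran from the new baseline.** With L = 0 the new baseline is week 6, its 6-week measure falls at week 12 and its 12-week measure at week 6 + 12 = 18. All 6 treatment weeks and 6 post-treatment weeks are then covered, as in the immediate arm. With lag, the last measure falls at week 18 + L.

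**Size of the final group.** Two cohorts of 30 + 30 (section 12.2) give 2 × 60 = 120, the planned total. The final delayed group is then 30 of 60 DTC participants, or 30 / 120 = 25% of eventual recipients. Section 9.1 speaks of three iterations, and 3 × 60 = 180 does not match 120. Taken literally, it makes the final group 30 of 90 DTC participants.

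**The case against.** The strongest reply is that the protocol's own timetable covers the delayed treatment: 6 + 6 = 12, so all 6 weeks fall inside the window. That stands. A reader might infer that much of the delayed arm's exposure goes unmonitored, but this needs a lag whose length appears nowhere. One could divide 28 weeks by two cohorts and suppose that early entrants wait up to 14 weeks. The protocol gives no such filling period, and it uses 28 weeks both for first session to final follow-up (section 5) and for recruitment (section 12.2).

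Second, section 13.3 does not name the baseline. Because the rows for delayed participants have their own baseline, the window could be read as running from it, and sections 13.3 and 13.4 could bring events in at those assessments. This is a possible reading. However, the procedures schedule, Table 11 and section 14.3.2 set out one baseline and nothing after week 12, so it cannot be relied on.

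Third, other channels exist: participant-initiated reports (13.3), risk raised with the supporting practitioner (14.3), and follow-up of alerts within 1 working day (14.10). Deaths (13.5) and reported adverse reactions (13.7) have no cut-off of their own. It would therefore be wrong to say that late harm could not surface. These channels do not replace scheduled questions put to everyone.

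Fourth, a reader might take the statement in section 9.1 to mean that the final delayed group has no safety collection at all. The text does not say so: if that group starts at week 6, its treatment still falls within 12 weeks of its original baseline. What stands is that no event reporting is stated for that treatment.

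Finally, this is a feasibility study of written self-help that the protocol regards as low risk. That limits the weight of the point but does not remove it.

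**Conclusion.** The point holds as a gap in the stated safety window. Taking the one baseline in the schedule, DTC participants have 0 post-treatment weeks of event reporting at any lag, against 6 in the immediate arm with no lag. Their 6 treatment weeks are fully covered only if there is no lag, and each week of lag removes one. The lag is unknown, so the loss of treatment weeks is a vulnerability and not an established amount. The assessments to about week 18 or later that Appendix 1 lists for these participants have no reporting period extended to them. The status of the final delayed group (30 of 60 DTC participants under the two-cohort plan) is unspecified.

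The documents do not support the stronger conclusions that most delayed exposure is unobserved or that the final group is wholly unmonitored. The correction is still worth making: following the window as written gives unequal, possibly truncated, harm data for half of the recipients, and the forms and visits needed already exist.

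**What to change.** - In section 13.3, the procedures schedule (Table 9, section 8.11) and section 14.3.2, state that for DTC participants the reporting period runs through the final assessment listed for them in Appendix 1 after they move to the intervention. Attach the existing event and risk questions to those assessments.
- State whether the deterioration intervals in section 13.2 also apply between the new assessments.
- Tabulate events by exposure period (before, during and after the intervention) as well as by randomised arm.
- Reconcile section 9.1 with sections 9.2 and 10.1 and Appendix 1. Say either that the final DTC group is covered by the same assessments or that its treatment is not counted as trial exposure.

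**Cost.** Wording, and reuse of existing questions at assessments already listed. Event collection closes about 6 or more weeks later for DTC participants. If the final group is covered, the 28-week period in section 5 is affected. With no further lag, a last DTC measure 18 weeks after the second cohort's first session fits only if that session is held by week 28 − 18 = 10. If that session is at week 28 − 12 = 16, the latest that fits the present 12-week follow-up, collection would run to about week 16 + 18 = 34.

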13.4 Responsibilities

Researchers at central site (University of Exeter) to check for SAEs, AEs and ARs when participants complete treatment or at follow-up, potentially in response to automated feedback from website.

Chief Investigator (CI) is responsible via liaison with research team at central site for:

- 1. Ensuring that all SAEs are recorded in EDC and reported to the ExeCTU Trial Manager within 24 working hours / 1 working day of becoming aware of the event and provide further follow-up information as soon as available.
- 2. Ensuring that SAEs are chased with ExeCTU Trial Manager if a record of receipt is not received within 2 working days of initial reporting.
- 3. Ensuring that AEs and ARs are recorded and reported to the ExeCTU Trial Manager in line with the requirements of the protocol.
- 4. Immediate review of all SUSARs.
- 5. Review of specific SAEs and SARs in accordance with the trial risk assessment and protocol as detailed in the Trial Monitoring Plan.

Sponsor (NB where relevant these can be delegated to CI and trial manager) is responsible for:

- 1. Central data monitoring and verification of AEs, ARs, SAEs, SARs and SUSARs according to the trial protocol within the database (EDC).
- 2. Reporting safety information to the CI, delegate or independent clinical reviewer for the ongoing assessment of the risk / benefit according to the Trial Monitoring Plan.
- 3. Reporting SAEs that are related to the trial and unexpected, by email to the research ethics committee.
- 4. Reporting SAEs that are related to the trial and unexpected, by email to the research ethics committee.
- 5. Reporting safety information to the independent oversight committees identified for the trial (Data Monitoring Ethics Committee (DMEC) and / or Trial Steering Committee (TSC)) according to the Trial Monitoring Plan.
- 6. Expedited reporting of SUSARs to the Competent Authority (MHRA in UK) and REC within required timelines.
- 7. Notifying Investigators of SUSARs that occur within the trial.
- 8. Preparing standard tables and other relevant information in collaboration with the CI and ensuring timely submission to the MHRA and REC.

13.5 Notification of deaths

All deaths will be reported to the ExeCTU Trial Manager who will report to the Sponsor, irrespective of whether the death is related to the trial or an unrelated event. If the event is unrelated to the feasibility trial then this will be reported to the sponsor within one week, and if it thought to be related to the trial the report will be submitted within 2 working days.

